11.0 Analysis Sets

Analysis Set	Definition	Use	How Analyzed
Safety	All subjects who received at least one dose of study drug.	Safety and tolerability	According to actual treatment received
ITT	All subjects who are randomized.	PD and Efficacy	According to randomized treatment assigned

Analysis Set	Definition	Use	How Analyzed
miITT	All subjects who are randomized and received at least one dose of study drug. If all randomized subjects are dosed, the miITT Analysis Set will not be created and the ITT Analysis Set will be used.	PD and Efficacy	According to randomized treatment assigned
PP	All subjects in the Safety Analysis Set who have provided sufficient data without major protocol deviations or events that would be expected to affect the analysis. Sufficient data is defined as any post-baseline assessment and subject did not discontinue prior to Week 12 for reasons other than AEs.	PD and Efficacy	According to actual treatment received
PK (Analysis)	All subjects in the Safety Analysis Set who have received at least 1 dose of IMR-687 and have any measurable postdose IMR-687 concentration-time data.	PK concentrations	According to actual treatment received
PK (Evaluable)	All subjects in the Safety Analysis Set who have received at least 1 dose of IMR-687 and have at least 4 consecutive non-zero postdose IMR-687 concentration-time data points.	PK parameters	According to actual treatment received

11.1 Safety Analysis Set

The Safety Analysis Set will include all subjects who have received at least one dose of study drug and will be used to summarize all safety and tolerability data. In safety summaries, subjects will be analyzed according to the actual treatment they received.

11.2 Intent-to-Treat Analysis Set

The ITT Analysis Set will include all subjects who are randomized. Subjects will be analyzed according to their randomized treatment. The ITT Analysis Set will be used for PD and efficacy analyses.

11.3 Modified Intent-to-Treat Analysis Set

In the event that any subjects are randomized but not dosed, a miITT Analysis Set will be created that will include all subjects who are randomized and receive at least one dose of study drug. Subjects will be analyzed according to their randomized treatment. The miITT Analysis Set will be used for PD and efficacy analyses.

11.4 Per Protocol Analysis Set

The Per Protocol Analysis Set will include all subjects in the Safety Analysis Set who have provided sufficient data without major protocol deviations or events that would be expected to affect the analysis. Sufficient data is defined as any post-baseline assessment and subject did not discontinue prior to week 12 for reasons other than AEs. The PP Analysis Set will be identified based on blinded data prior to unblinding the final analysis dataset, and the TDT and NTDT populations may have their PP Analysis Set components defined at different times. The PP Analysis Set will be the primary analysis set used for PD and efficacy analyses. Subjects will be analyzed according to their randomized treatment.

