13.6 Endpoint Analyses

Endpoint analyses for TDT and NTDT populations will be reported separately. All efficacy endpoints will be conducted using the PP Analysis Set and may be repeated for the mITT Analysis Set (if applicable), and the ITT Analysis Set (where applicable).

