13.6.4 Efficacy Analyses (Secondary Endpoints)

The PP Analysis Set will be used for all efficacy endpoint analyses. Selected analyses will be repeated on the mITT and/or ITT Analysis Sets as sensitivity analyses, with mITT only used if different than the ITT. The TDT and NTDT populations will be summarized separately for all analyses.

Table 8 Secondary Endpoints – TDT Population

Secondary Endpoints	Time Points	Secondary Endpoint Analysis
Proportion of subjects with a $\geq 20\%$ reduction in RBC transfusion burden with a reduction of at least 2 units of RBCs (hematological improvement)	Fixed time periods of Week 12 to Week 24, Week 24 to Week 36, and Week 12 to Week 36, compared to the 12-week interval prior to Baseline (Day 1)	
 • Cochran-Mantel Haenszel (CMH) analysis: Odds ratios (OR) (active arms vs. placebo), 2-sided 95% CI, p-value • Summary of number and percentage of responders with difference in proportions (active arm-Placebo) and corresponding 2-sided 95% CI • Forest plots of ORs, 2-sided 95% CIs, p-value – Higher dose vs. placebo, Lower dose vs. placebo
Proportion of subjects with a $\geq 33\%$ reduction in RBC transfusion burden with a reduction of at least 2 units of RBCs (hematological improvement)		
Proportion of subjects with a $\geq 50\%$ reduction in RBC transfusion burden with a reduction of at least 2 units of RBCs (hematological improvement)		
Proportion of subjects with a $\geq 20\%$ reduction in RBC transfusion burden with a	Rolling 12-week time periods –	

reduction of at least 2 units of RBCs (hematological improvement)	Day 2 to 85, Day 3 to 86, etc. through Day 170 to Day 253 (Week 36), compared to the 12-week interval prior to Baseline (Day 1)	
Proportion of subjects with a $\geq 33\%$ reduction in RBC transfusion burden with a reduction of at least 2 units of RBCs (hematological improvement)	Rolling 14-week time periods – Day 2 to 99, Day 3 to 100, etc. through Day 156 to Day 253 (Week 36), compared to the 12-week interval prior to Baseline (Day 1)	

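### Most efficacy and PD comparisons with placebo lead with a Per Protocol set that drops early non-AE dropouts, and the SAP gives two rules for grouping that set

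*SAP*

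**What the plan says.** SAP 11.4 makes PP the lead set for efficacy and PD: "The PP Analysis Set will be the primary analysis set used for PD and efficacy analyses". Section 13.6.4 repeats this for the secondary endpoints ("The PP Analysis Set will be used for all efficacy endpoint analyses"), and 13.6.6 does so for the exploratory ones.

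PP starts from the Safety Analysis Set. It requires sufficient data and no major deviations or events expected to affect the analysis. Sufficient data means any post-baseline assessment, and that the "subject did not discontinue prior to week 12 for reasons other than AEs".

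ITT has a secondary but planned role. Section 13.6.4 says: "Selected analyses will be repeated on the mITT and/or ITT Analysis Sets as sensitivity analyses, with mITT only used if different than the ITT". Section 13.6 is looser and makes the repeat optional. In Tables 3 and 4 of Section 12.0, PP and ITT stand side by side for most efficacy outputs at IA 2.0 and the final analysis. At IA 0.5 the efficacy tables are PP only. At IA 1.0 they are PP only except for three NTDT Week 24 responder sensitivity tables.

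PP does not lead everywhere. Section 13.6.4.1 puts the ANCOVAs of iron chelation dose and serum ferritin on the Safety set, although Tables 3 and 4 list PP and ITT for them. Tables 3 and 4 list the TranQOL, SF-36 and NTDT-PRO outputs on ITT.

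On grouping, the PP row of the 11.0 table reads "According to actual treatment received", while 11.4 reads "Subjects will be analyzed according to their randomized treatment".

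**The concern.** These are two-sided tests of each active arm against placebo for a difference, with no non-inferiority margin, so the usual reason for leading with PP does not arise. Selecting subjects on what happens after randomization can make the arms unlike each other, because early dropout can itself depend on treatment. The rule is also uneven: leaving before Week 12 for an AE keeps a subject in, and leaving for any other reason takes the subject out.

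If the removed subjects are mainly non-responders and more of them come from one arm, that arm's response rate rises for reasons unrelated to the drug. Readers of the early interim tables would mostly have no ITT result beside it.

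The grouping contradiction is a separate fault. If anyone receives a treatment other than the one assigned, the two rules give different tables, and a programmer cannot follow both.

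**Working it through.** **1. The plan's own power figures.** SAP 8.1.1 and 8.1.2 assume 10% response on placebo and 50% on active at two-sided alpha 0.05, and state about 79% power (TDT, 30 active and 20 placebo) and 67% (NTDT, 30 and 15). A continuity-corrected two-proportion z-test reproduces both:

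power = Φ{[|p1 − p2| − ½(1/n1 + 1/n2) − 1.96·SE0] / SE1}, with SE0 from the pooled rate and SE1 from the separate rates.

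- TDT: pooled rate (15 + 2)/50 = 0.34; SE0 = √(0.34 × 0.66 × 0.0833) = 0.1367; SE1 = √(0.25/30 + 0.09/20) = 0.1133. (0.40 − 0.0417 − 0.2680)/0.1133 = 0.797, so power is 78.7%.
- NTDT: pooled rate (15 + 1.5)/45 = 0.367; SE0 = 0.1524; SE1 = 0.1197. (0.40 − 0.05 − 0.2987)/0.1197 = 0.429, so power is 66.6%.

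These figures use the full arm sizes, with no allowance for PP exclusions.

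**2. What exclusion does to a response rate.** Let p be the true response rate among all randomized subjects and d the fraction excluded, and assume that every excluded subject is a non-responder. The PP rate is then p/(1 − d). The documents give no value for d, so all values below are assumptions. True response is 30% in both arms, so there is no real effect.

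| Excluded, active / placebo | PP rate, active | PP rate, placebo |
|---|---|---|
| 10% / 10% | 0.30/0.90 = 33.3% | 33.3% |
| 15% / 5% | 0.30/0.85 = 35.3% | 0.30/0.95 = 31.6% |
| 25% / 5% | 0.30/0.75 = 40.0% | 31.6% |
| 10% / 20% | 33.3% | 0.30/0.80 = 37.5% |

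Equal exclusion leaves equal rates equal. Unequal exclusion moves the comparison in either direction, depending on which arm loses more.

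**3. Chance of a false result favouring active.** This sums binomial probabilities over all tables in which the CMH chi-square test rejects at two-sided 0.05 in favour of active.

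- 30 versus 20: 2.2% with no exclusion. With 25% versus 5% excluded, 7.8% if 22 active and 19 placebo subjects remain (7.4% if 23 and 19, since 30 × 0.75 = 22.5).
- 30 versus 15: 2.1% with no exclusion. With 25% versus 5% excluded, 5.9% if 22 and 14 remain (7.0% if 23 and 14).
- With 15% versus 5% excluded the figure is about 4% in either population.

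**4. What leading with ITT costs in power.** This uses the formula of step 1, the same dropout fraction in both arms and no replacement. PP drops the subjects and keeps 10%/50%; ITT keeps them as non-responders.

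| Dropout | TDT, PP | TDT, ITT | NTDT, PP | NTDT, ITT |
|---|---|---|---|---|
| 5% | 75.7% | 74.4% | 63.1% | 61.5% |
| 10% | 72.4% | 69.8% | 59.3% | 56.3% |
| 20% | 64.8% | 59.7% | 51.1% | 45.7% |

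**5. Why a dropout rule is needed as well.** Protocol 8.5.1 withdraws from the study anyone who discontinues study drug, and SAP 13.6.3 generally imputes nothing. SAP 13.6.4.1 defines TDT response from the sum of units in the window. A subject gone before Week 12 has no recorded on-study units after leaving, and the SAP does not say whether that is missing or a full reduction. Renaming the lead set would leave this open.

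**The case against.** The trial's primary objective is safety, analysed on the Safety set, and the efficacy tests are secondary or exploratory and unadjusted for multiplicity. Protocol 13.2 and 13.4 already gave PP a role in efficacy, beside the safety population, and the SAP improved on this by adding ITT and mITT. PP is fixed on blinded data before the final unblinding. All of this stands, and it limits how much rests on the choice of set. It does not remove the problem: blinded selection stops anyone choosing subjects by arm, but it cannot correct for dropout that already differs by arm. The SAP also does not say how PP membership is fixed for the earlier unblinded interim analyses that use it.

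Three stronger readings are tempting, and the documents do not support them.

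- A reader might infer that every comparison leads with PP, or that ITT might never be run. Section 13.6.4.1, Tables 3 and 4 and the planned repeats in 13.6.4 show otherwise.
- A reader might infer that the removed subjects are mostly treatment failures. Protocol 8.4 gives a non-exhaustive list of reasons for discontinuation that does not mention lack of benefit, and no dropout rate is given. The 10-of-60 replacement allowance in Protocol 8.6 is a ceiling, not a rate, and it also covers AE dropouts.
- A reader might take a growing difference as proof of unequal bias. If 5 of 30 active and 3 of 20 placebo non-responders leave, 15/30 versus 2/20 (40 points) becomes 15/25 versus 2/17 (60% versus 12%, 48 points). Those exclusions are nearly equal (17% and 15%), so this is mainly both rates rescaled by about the same factor.

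**Conclusion.** The point holds for the efficacy and PD comparisons that lead with PP, which are most but not all of them. It should be corrected, but it does not touch the primary safety analysis. The size of any bias is unknown. It is nil if true rates and exclusion are equal in the arms. It reaches about 8 points (40% versus 32%) under a deliberately unequal assumption of 25% versus 5% excluded, all non-responders, at 30% true response. In that case the chance of a false result favouring active rises from about 2% to about 7–8% (TDT sizes) or 6–7% (NTDT sizes). More exclusion on placebo would bias the other way. The grouping contradiction between 11.0 and 11.4 needs no assumption and must be reconciled in any case.

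**What to change.** In SAP 11.0, 11.4, 13.6, 13.6.4, 13.6.6 and Tables 3 and 4:

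- Make ITT (or mITT), by randomized treatment, the lead set for the efficacy comparisons that now lead with PP, at the interim and final analyses. Keep PP as a sensitivity analysis, and align the defaults in 13.6.4.4 and 13.6.6.4.
- For the responder endpoints, state that subjects without data for the response window because of discontinuation count as non-responders.
- Change the PP row of the 11.0 table so that table and text both say randomized treatment.

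For continuous endpoints the change of set adds little for early dropouts, whose window data are missing and generally not imputed.

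The cost is SAP wording and a few extra ITT outputs at IA 0.5 and IA 1.0, since ITT is already defined and listed for most later tables. Response rates and effects may look slightly smaller, and under the assumptions above power falls by about 1 to 5 points relative to PP.

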11.5 PK Analysis Set

The PK Analysis Set will be defined as all subjects in the Safety Analysis Set who are randomized, have received at least 1 dose of IMR-687, and have any measurable postdose IMR-687 concentration data. The PK Analysis Set will be used to generate the corresponding PK concentration summaries and plots.

11.6 PK Evaluatable Set

The PK Evaluatable Set will be defined as all subjects in the Safety Analysis Set who are randomized, have received at least 1 dose of IMR-687, and have at least 4 consecutive non-zero postdose IMR-687 concentration-time data points. The PK Evaluatable Set will be used to generate the corresponding PK parameter assessments.

12.0 Interim Analyses

There will be five unblinded interim analyses (IA) conducted at each of the following milestones:

- IA 0.5: Approximately 15 subjects in the NTDT population have completed 12 weeks of treatment
- IA 1.0:
 - Approximately 30 subjects in the TDT population have completed 24 weeks of treatment
 - Approximately 30 subjects in the NTDT population have completed 24 weeks of treatment
- IA 2.0:
 - Approximately 60 subjects in the TDT population have completed 24 weeks of treatment
 - Approximately 60 subjects in the NTDT population have completed 24 weeks of treatment

To facilitate the IAs, certain Sponsor representatives and designees may be unblinded to individual treatment assignments prior to and during the IA (including the unblinded clinical research organization (CRO) biostatistician and external groups for bioanalytical, PK, PK/PD analyses, and QoL analyses). Details are provided in the study unblinding plan. The blinded Sponsor and CRO study team members may be unblinded to the group analysis results (but not individual subject results) at the conclusion of the IA(s).

The IA(s) will include the primary endpoint analyses, selected secondary/ exploratory endpoint analyses and baseline summaries. The IA analyses will be performed by an unblinded statistical and programming team. No alpha spending will be used.

The following is a summary of the key IA tables and figures that will be provided at each IA. Additional IA analyses may be added/provided per Imara request/decision. More detailed analyses information will be provided in section 13.0 of the SAP.

No minimum and maximum values will be populated on tables and no scattered values will be populated on the boxplots, in order to ensure that group blinding is maintained. Further, to avoid unblinding, at IA's 0.5 and 1.0, adverse event tables will only present Placebo and pooled IMR-687 dose columns. In the Overall Summary of Treatment-Emergent Adverse Events tables, only AE categories with 10% or higher in the pooled IMR-687 dose column will be presented. In the remaining Adverse Events tables, only preferred terms with 10% or higher in the pooled IMR-687 dose column will be presented. Imara Blinded team members will only be group unblinded and cannot be exposed to that information as it could be potentially unblinding.

Table 3: Interim Analysis Tables – TDT Population

Outputs	Analysis Number	Timepoints	Analysis Set(s)
Tables			
Subject Disposition	IA 1.0, 2.0 FA	N/A	All Screened Subjects
Demographics and Baseline Characteristics	IA 1.0, 2.0 FA	N/A	Safety Analysis Set
Disease History	IA 1.0, 2.0 FA	N/A	Safety Analysis Set
Proportion of subjects with $\geq 20\%$, 33% , and 50% reduction in RBC transfusion burden with a reduction of at least 2 units of RBCs (hematological improvement) – fixed time periods	IA 1.0 IA 2.0 FA	Week 12 to 24 Week 12 to 24 Week 12 to 24, Week 24 to 36, Week 12 to 36	Per Protocol Analysis Set Per protocol analysis set/ ITT analysis set Per protocol analysis set/ ITT (mITT) Analysis Set
Proportion of subjects with $\geq 20\%$, 33% , and 50% reduction in RBC transfusion burden with a reduction of at least 2 units of RBCs (hematological improvement) – rolling time periods	IA 1.0 IA 2.0 FA	Rolling time periods – Days 2 to 85, Day 3 to 86 and so on through Day 86 to 169, compared to the 12-week interval prior to Baseline (Day 1) Rolling time periods – Days 2 to 85, Day 3 to 86 and so on through Day 86 to 169, compared to the 12-week interval prior to Baseline (Day 1) Rolling time periods – Days 2 to 85, Day 3 to 86 and so on through Day 170 to 253 (Week 36), compared to the 12-week interval prior to Baseline (Day 1)	Per Protocol Analysis Set Per Protocol Analysis Set/ ITT Analysis Set Per Protocol Analysis Set/ ITT (mITT) Analysis Set
Change and Percent Change from Baseline in mean Hb, Specialty Hematology, and PD parameters (listed in Sections 13.6.7 and 13.6.8)	IA 1.0	1. Week 12 to 24 Mean 2. Descriptive statistics by visit	Per Protocol Analysis Set

Outputs	Analysis Number	Timepoints	Analysis Set(s)
	IA 2.0	1. Week 12 to 24 Mean 2. Descriptive statistics by visit 3. MMRM of all visits up to Week 24 (Change only)	Per Protocol Analysis Set/ ITT Analysis Set
	FA	1. Week 12 to 24 Mean, Week 24 to 36 Mean 2. Descriptive statistics by visit 3. MMRM of all visits up to Week 36 (Change only)	Per Protocol Analysis Set/ ITT (mITT) Analysis Set
Mean number of transfusion events	IA 2.0	Through Week 24	Per Protocol Analysis Set/ ITT Analysis Set
	FA	Through Week 36	Per Protocol Analysis Set/ ITT (mITT) Analysis Set
Mean change in transfusion burden	IA 2.0	Week 12 to Week 24, compared to the 12-week prior to Baseline (Day 1)	Per Protocol Analysis Set/ ITT Analysis Set
	FA	Week 12 to Week 24, Week 24 to Week 36, and Week 12 to Week 36, compared to the 12-week prior to Baseline (Day 1)	Per Protocol Analysis Set/ ITT (mITT) Analysis Set
Proportion of subjects who are transfusion-free (independent) for ≥ 8 weeks during treatment	IA 2.0	Through Week 24	Per Protocol Analysis Set/ ITT Analysis Set
	FA	Through Week 36	Per Protocol Analysis Set/ ITT (mITT) Analysis Set
Proportion of subjects who are RBC transfusion-free (independent)	IA 2.0	Over 24 Weeks	Per Protocol Analysis Set/ ITT Analysis Set
	FA	Over 36 Weeks	Per Protocol Analysis Set/ ITT (mITT) Analysis Set
Average number of days between transfusions	IA 2.0	Through Week 24	Per Protocol Analysis Set/ ITT Analysis Set
	FA	Over 36 weeks	Per Protocol Analysis Set/ ITT (mITT) Analysis Set
Change from Baseline in mean pre-transfusion Hb values at Weeks 12 to 24 [using pre-transfusion Hb from the Historical Transfusion Burden and the Transfusion Burden CRFs]	IA 2.0	Baseline to Week 12 to Week 24	Per Protocol Analysis Set/ ITT Analysis Set
	FA	Baseline to Week 12 to Week 24, Week 24 to Week 36, and Week 12 to Week 36	Per Protocol Analysis Set/ ITT (mITT) Analysis Set
Proportion of subjects with an increase from Baseline of ≥ 1.0 g/dL in mean pre-transfusion Hb	IA 2.0	Week 12 to Week 24	Per Protocol Analysis Set/ ITT Analysis Set

Outputs	Analysis Number	Timepoints	Analysis Set(s)
values or a Reduction in RBC Transfusion Burden ($\geq 33\%$ reduction) Endpoint [using pre-transfusion Hb from the Historical Transfusion Burden and the Transfusion Burden CRFs]	FA	Week 24 to Week 36, Week 12 to Week 36	Per Protocol Analysis Set/ ITT (mITT) Analysis Set
Mean change from Baseline for Serum ferritin	IA 1.0	Week 24	Per Protocol Analysis Set
	IA 2.0	Week 24	Per Protocol Analysis Set/ ITT Analysis Set
	FA	Week 24, 36	Per Protocol Analysis Set/ ITT (mITT) Analysis Set
Mean change from Baseline for Iron chelation therapy daily dose	IA 2.0	Week 24	Per Protocol Analysis Set/ ITT Analysis Set
	FA	Week 24, 36	Per Protocol Analysis Set/ ITT (mITT) Analysis Set
Mean change from Baseline in TranQOL quality of life tool	IA 2.0	Weeks 12, 24	ITT Analysis Set
	FA	Weeks 12, 24, and 36	ITT (mITT) Analysis Set
Mean change from Baseline in SF-36 quality of life	IA 2.0	Weeks 12, 24	ITT analysis set
	FA	Weeks 12, 24, and 36	ITT (mITT) Analysis Set
Summary of exposure	IA 1.0, 2.0	All available data up to Week 24 at the time of IA	Safety Analysis Set
	FA	All available data	Safety Analysis Set
Overall summary of TEAEs	IA 1.0, 2.0	All available data up to Week 24 at the time of IA	Safety Analysis Set
	FA	All available data	Safety Analysis Set
TEAEs by SOC & PT	IA 1.0, 2.0	All available data up to Week 24 at the time of IA	Safety Analysis Set
	FA	All available data	Safety Analysis Set
TEAEs by PT	IA 1.0, 2.0	All available data up to Week 24 at the time of IA	Safety Analysis Set
	FA	All available data	Safety Analysis Set
Drug-related TEAEs by SOC & PT	IA 1.0, 2.0	All available data up to Week 24 at the time of IA	Safety Analysis Set
	FA	All available data	Safety Analysis Set
Drug-related TEAEs by PT	IA 1.0, 2.0	All available data up to Week 24 at the time of IA	Safety Analysis Set
	FA	All available data	Safety Analysis Set
TEAEs by SOC, PT & severity	IA 1.0, 2.0	All available data up to Week 24 at the time of IA	Safety Analysis Set
	FA	All available data	Safety Analysis Set

Outputs	Analysis Number	Timepoints	Analysis Set(s)
Mean pharmacokinetic parameters for IMR-687 by dose and by study visit	IA 1.0	All available data up to Week 24	PK Evaluable Set
	FA	All available data	PK Evaluable Set
Figures			
Bar plot of proportion of subjects with reduction in RBC transfusion burden (hematological improvement) by treatment arm	IA 1.0	Week 12 to 24	Per Protocol Analysis Set
	IA 2.0	Week 12 to 24	Per Protocol Analysis Set/ ITT Analysis Set
	FA	Week 12 to 24, Week 24 to 36, Week 12 to 36	Per Protocol Analysis Set/ ITT (mITT) Analysis Set
Arithmetic mean (\pm SD) plasma concentration of IMR-687 by dose and by study visit (linear and semi-logarithmic scale)	1.0	All available data up to Week 3	PK Analysis Set
	FA	All available data	PK Analysis Set

Table 4: Interim Analysis Tables – NTDT Population

Outputs	Analysis Number	Timepoints	Analysis Set(s)
Tables			
Subject Disposition	IA 0.5, 1.0, 2.0 FA	N/A	All Screened Subjects
Demographics and Baseline Characteristics	IA 0.5, 1.0, 2.0 FA	N/A	Safety Analysis Set
Disease History	IA 0.5, 1.0, 2.0 FA	N/A	Safety Analysis Set
Responder analysis - Analysis of proportion of subjects with $\geq 3\%$ increase from baseline in mean HbF in the absence of transfusions	IA 0.5, 1.0	Week 12 to Week 24	Per Protocol Analysis Set
	IA 2.0	Week 12 to Week 24	Per Protocol Analysis Set/ ITT Analysis Set
	FA	Week 12 to Week 24, and Week 24 to Week 36	Per Protocol Analysis Set/ ITT (mITT) Analysis Set
Responder analysis - Analysis of proportion of subjects with $\geq 3\%$ increase from baseline in HbF in the absence of transfusions [sensitivity analysis]	IA 1.0, 2.0	Week 24	Per Protocol Analysis Set/ ITT Analysis Set
	FA	Week 24, Week 36	Per Protocol Analysis Set/ ITT (mITT) Analysis Set
Responder analysis - Analysis of proportion of subjects with ≥ 1.0 g/dL increase from baseline in mean Hb in the absence of transfusions	IA 0.5, 1.0	Week 12 to Week 24	Per Protocol Analysis Set
	IA 2.0	Week 12 to Week 24	Per Protocol Analysis Set/ ITT Analysis Set
	FA	Week 12 to Week 24, and Week 24 to Week 36	Per Protocol Analysis Set/ ITT (mITT) Analysis Set
Responder analysis - Analysis of proportion of subjects with ≥ 1.0 g/dL increase from baseline	IA 1.0, 2.0	Week 24	Per Protocol Analysis Set/ ITT Analysis Set

Outputs	Analysis Number	Timepoints	Analysis Set(s)
in Hb in the absence of transfusions [sensitivity analysis]	FA	Week 24, Week 36	Per Protocol Analysis Set/ ITT (mITT) Analysis Set
Responder analysis - Analysis of proportion of subjects with ≥ 1.5 g/dL increase from baseline in mean Hb in the absence of transfusions	IA 0.5, 1.0	Week 12 to Week 24	Per Protocol Analysis Set
	IA 2.0	Week 12 to Week 24	Per Protocol Analysis Set/ ITT Analysis Set
	FA	Week 12 to Week 24, and Week 24 to Week 36	Per Protocol Analysis Set/ ITT (mITT) Analysis Set
Responder analysis - Analysis of proportion of subjects with ≥ 1.5 g/dL increase from baseline in Hb in the absence of transfusions [sensitivity analysis]	IA 1.0, 2.0	Week 24	Per Protocol Analysis Set/ ITT Analysis Set
	FA	Week 24, Week 36	Per Protocol Analysis Set/ ITT (mITT) Analysis Set
Proportion of subjects who have an Hb increase of ≥ 1.0 g/dL from Baseline for ≥ 14 days in the absence of RBC transfusions	IA 2.0	14-day periods through Week 24	Per Protocol Analysis Set/ ITT Analysis Set
	FA	14-day periods through Week 36	Per Protocol Analysis Set/ ITT (mITT) Analysis Set
Change and Percent Change from Baseline in mean Hb, Specialty Hematology, and PD parameters (listed in Sections 13.6.7 and 13.6.8)	IA 0.5, 1.0	1. Week 12 to 24 Mean 2. Descriptive statistics by visit	Per Protocol Analysis Set
	IA 2.0	1. Week 12 to 24 Mean 2. Descriptive statistics by visit 3. MMRM of all visits up to Week 24 (Change only)	Per Protocol Analysis Set/ ITT Analysis Set
	FA	1. Week 12 to 24 Mean, Week 24 to 36 Mean 2. Descriptive statistics by visit 3. MMRM of all visits up to Week 36 (Change only)	Per Protocol Analysis Set/ ITT (mITT) Analysis Set
Duration of the mean Hb increase from Baseline of ≥ 1.0 g/dL	IA 2.0	Over 24 weeks from Baseline	Per Protocol Analysis Set/ ITT Analysis Set
	FA	Over 36 weeks from Baseline	Per Protocol Analysis Set/ ITT (mITT) Analysis Set
Proportion of subjects who are transfusion-free (independent) for ≥ 8 weeks during treatment	IA 2.0	Through Week 24	Per Protocol Analysis Set/ ITT Analysis Set
	FA	Through Week 36	Per Protocol Analysis Set/ ITT (mITT) Analysis Set
Proportion of subjects who are RBC transfusion-free (independent)	IA 2.0	Over 24 weeks	Per Protocol Analysis Set/ ITT Analysis Set
	FA	Over 36 weeks	Per Protocol Analysis Set/ ITT (mITT) Analysis Set
Mean change from Baseline for Serum ferritin	IA 0.5	Week 24	Per Protocol Analysis Set

Outputs	Analysis Number	Timepoints	Analysis Set(s)
	IA 1.0	Week 24	Per Protocol Analysis Set
	IA 2.0	Week 24	Per Protocol Analysis Set/ ITT Analysis Set
	FA	Week 24, 36	Per Protocol Analysis Set/ ITT (mITT) Analysis Set
Mean change from Baseline for Iron chelation therapy daily dose	IA 2.0	Week 24	Per Protocol Analysis Set/ ITT Analysis Set
	FA	Week 24, 36	Per Protocol Analysis Set/ ITT (mITT) Analysis Set
Change from Baseline in SF-36 quality of life	IA 2.0	Weeks 12, 24	ITT Analysis Set
	FA	Weeks 12, 24, 36	ITT (mITT) Analysis set
Change from Baseline in mean NTDT-PRO total score and domain scores including tiredness/weakness domain over a continuous 12-week interval	IA 2.0	Week 12 to Week 24	ITT Analysis Set
	FA	Week 12 to Week 24, Week 24 to Week 36	ITT (mITT) Analysis Set
Change from Baseline in NTDT-PRO total score and domain score including tiredness/weakness domain	IA 2.0	Week 24	ITT Analysis Set
	FA	Weeks 24, 36	ITT (mITT) Analysis Set
Summary of exposure	IA 0.5, 1.0, 2.0	All available data up to Week 24 at the time of IA	Safety Analysis Set
	FA	All available data	Safety Analysis Set
Overall summary of TEAEs	IA 0.5, 1.0, 2.0	All available data up to Week 24 at the time of IA	Safety Analysis Set
	FA	All available data	Safety Analysis Set
TEAEs by SOC & PT	IA 0.5, 1.0, 2.0	All available data up to Week 24 at the time of IA	Safety Analysis Set
	FA	All available data	Safety Analysis Set
TEAEs by PT	IA 0.5, 1.0, 2.0	All available data up to Week 24 at the time of IA	Safety Analysis Set
	FA	All available data	Safety Analysis Set
Drug-related TEAEs by SOC & PT	IA 0.5, 1.0, 2.0	All available data up to Week 24 at the time of IA	Safety Analysis Set
	FA	All available data	Safety Analysis Set
Drug-related TEAEs by PT	IA 0.5, 1.0, 2.0	All available data up to Week 24 at the time of IA	Safety Analysis Set
	FA	All available data	Safety Analysis Set
TEAEs by SOC, PT & severity	IA 0.5, 1.0, 2.0	All available data up to Week 24 at the time of IA	Safety Analysis Set
	FA	All available data	Safety Analysis Set

Outputs	Analysis Number	Timepoints	Analysis Set(s)
Mean pharmacokinetic parameters for IMR-687 by dose and by study visit	1.0	All available data up to Week 12	PK Evaluable Set
	FA	All available data	PK Evaluable Set
Figures			
Line plot of mean change from Baseline in Hb & HbF by treatment arm	IA 1.0 [arithmetic]	Week 12 to 24	Per Protocol Analysis Set
	2.0 [Ismeans]	Week 12 to 24	Per Protocol Analysis Set/ ITT Analysis Set
	FA [Ismeans]	Week 12 to 24, Week 24 to 36	Per Protocol Analysis Set/ ITT (mITT) Analysis Set
Bar plot of proportion of subjects with ≥ 1.0 g/dL increase from baseline in mean Hb in the absence of transfusions	IA 1.0	Week 12 to 24	Per Protocol Analysis Set
	IA 2.0	Week 12 to 24	Per Protocol Analysis Set/ ITT Analysis Set
	FA	Week 12 to 24, Week 24 to 36	Per Protocol Analysis Set/ ITT (mITT) Analysis Set
Bar plot of proportion of subjects with $\geq 3\%$ increase from baseline in mean HbF in the absence of transfusions	IA 1.0	Week 12 to 24	Per Protocol Analysis Set
	IA 2.0	Week 12 to 24	Per Protocol Analysis Set/ ITT Analysis Set
	FA	Week 12 to 24, Week 24 to 36	Per Protocol Analysis Set/ ITT (mITT) Analysis Set
Arithmetic mean (\pm SD) plasma concentration of IMR-687 by dose and by study visit (linear and semi-logarithmic scale)	1.0	All available data up to Week 4	PK Analysis Set
	FA	All available data	PK Analysis Set

